5.4 Removal criteria

Samples that meet any of the following criteria are considered ineligible and should be excluded from the study; subjects whose samples have been excluded may continue to participate in the study if they have been resampled to obtain an eligible sample:

- ✓ Insufficient sample size or visually significantly less than the sample size required for the program;
- ✓ The sample is contaminated;
- ✓ Watery stools;
- ✓ A sample that is loose stool and does not contain any formed portion;
- ✓ Mucus or pus stools;
- ✓ Bloody stools;
- Subjects with failed sample unwilling to cooperate with resampling;
- Subjects with inadequate bowel preparation or where the colonoscope does not reach the blind part of the model;
- Samples for which laboratory testing cannot be completed for unknown reasons;
- Subjects with an unclear diagnosis or incomplete case history;
- Subjects who are considered unsuitable for the study after full discussion with the investigator.

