6.7 Information entry and collation

Information including CRC risk questionnaire, subject code, age, gender, fecal-based miR-92a test results, FIT test results, colonoscopy and pathology results, and hospital discharge diagnosis or medical records will be aggregated by the investigator into the research database after removing personally identifiable information. Subject enrolment, sample testing and compilation of information will be conducted simultaneously to allow the investigator to provide timely feedback on subsequent enrolment based on sample collection and testing. Personal identification information includes, but is not limited to, the subject's name, ID card number, social security account number, driver's license number, clinic number, hospitalization number and any other information that can directly or indirectly identify the subject.

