7.1 Test termination points

7.1.1 Relevant definitions

The main objective of the study was to examine the performance of FIT, miR-92a, and FIT + miR-92a for AN. Colonoscopy and histopathology were used as the gold standard to determine the classification of the subject.

Sayooning toot	Colonoscopy and histopathology		
Screening test	Patients	Nonpatients	
Positive	True positive (TP)	False positive (FP)	
Negative	False negative (FN)	True negative (TN)	

When counting the performance of different screening protocols for CRC, subjects with a positive screening test result and a confirmed colonoscopy diagnosis of CRC were counted as true positives, otherwise they were counted as false positives, and subjects with a negative screening test and a confirmed colonoscopy diagnosis of a non-colorectal cancerous lesion, such as a normal, inflamed, polyps, advanced adenoma, or other non-colorectal cancerous lesion were counted as true negatives, otherwise they were counted as false negatives.

When counting the performance of different screening protocols for AN (CRC and AA), a positive screening test with a confirmed colonoscopy diagnosis of CRC or AA was counted as a true positive, otherwise it was counted as a

false positive, and a negative screening test with a confirmed colonoscopy diagnosis of a normal, inflamed, polyps, or other non-colorectal cancerous lesion was counted as a true negative, otherwise it was counted as a false negative.

Specific screening and analysis performance indicators are calculated as follows:

- Sensitivity (SN): also known as true positive rate (TPR), defined as true positive/ (true positive + false negative) × 100%;
- Specificity (SP): also known as true negative rate (TNR), defined as true negative/ (true negative + false positive) × 100%;
- Accuracy (ACC): defined as (true positive + true negative)/ (positive + negative) × 100%;
- Positive predictive value (PPV): defined as true positive/ (true positive + false positive) × 100%;
- Negative predictive value (NPV): defined as true negative/ (true negative + false negative) ×100%.

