7.1.3 Endpoint

The objective of the study is to analyze the performance of FIT, miR-92a and their combination for the detection of AN, evaluating performance indicators such as sensitivity, specificity, predictive values, diagnostic accuracy, likelihood ratios, and overall compliance rate, to formulate a strategy for early screening and prevention of CRC for an average-risk population. Once the project is initiated, the researchers will monitor the progress of enrolment, results of miR-92a and FIT, and colonoscopy and pathology results in real time, and will determine whether to terminate enrolment early based on the number of enrolments and fecal-based miR-92a positivity rate.

Data summaries for all subjects will be summarized in a frequency table:

	Colonoscopy	and/or histopatholog	T. 4-1	
Test result	CRC	AA	NEG	Total
Positive	a	b	c	a+b+c
Negative	d	e	f	d + e + f
Total	a + d	b + e	c + f	N

CRC colorectal cancer, AA advanced adenomas, NEG negative (including polyps, other non-colorectal cancerous lesion and no findings)

- (1) The sensitivity and specificity will be calculated as:
- xx test sensitivity for subjects with CRC = a/(a + d)
- xx test sensitivity for subjects with AA = b/(b + e)
- xx test sensitivity for subjects with AN = (a + b)/(d + e)
- xx test specificity for subjects with negative findings = f/(c + f)
- (2) The PPV and NPV will be calculated as:
- PPV (CRC) = Probability of having CRC given a positive xx test result = a/(a + b + c)
- PPV (AA) = Probability of having AA given a positive xx test result = b/(a + b + c)
- PPV (AN) = Probability of having AN given a positive xx test result = (a + b)/(a + b + c)
- NPV = Probability of having negative findings on colonoscopy given a negative xx test result = f/(d + e + f)
- (3) The LRs will be calculated as:
- PLR (CRC) = P (Test positive | CRC)/P (test positive | No CRC) = a/(b+c)
- PLR (AA) = P (Test positive | AA)/P (test positive | No AA) = b/(a + c)
- PLR (AN) = P (Test positive | AA or CRC)/P (test positive | No AA nor CRC) = (a + b)/c
- NLR (NEG) = P (Test negative | NEG)/P (test negative | AA or CRC) = f/(d + e)

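### Section 5.4 removes subjects for an incomplete or poorly prepared colonoscopy with no exception for confirmed CRC or AA, so known cases can drop out of sensitivity and detection rate

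*Protocol*

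**What the plan says.** Protocol section 5.4 opens with a rule about samples: "Samples that meet any of the following criteria are considered ineligible and should be excluded from the study". The list under it mixes sample faults with entries that name subjects. One of the latter is "Subjects with inadequate bowel preparation or where the colonoscope does not reach the blind part of the model". I take the garbled end of that entry to mean the caecum. The entry turns on examination quality alone and does not mention what the examination found.

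The only way back that 5.4 describes concerns stool: "subjects whose samples have been excluded may continue to participate in the study if they have been resampled to obtain an eligible sample".

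Section 7.1.1 defines cases by what was confirmed. For CRC, "subjects with a positive screening test result and a confirmed colonoscopy diagnosis of CRC were counted as true positives". The AN rule has the same form: "a positive screening test with a confirmed colonoscopy diagnosis of CRC or AA was counted as a" true positive. Neither rule requires a complete or well-prepared examination. Section 7.1.2 likewise classifies AA by the lesion found.

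Section 6.7 shows that the information needed to establish status is collected: "colonoscopy and pathology results, and hospital discharge diagnosis or medical records will be aggregated by the investigator".

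**The concern.** An incomplete or poorly prepared examination makes a negative finding unreliable, because part of the bowel was not seen. It does not undo a cancer or advanced adenoma already confirmed by histology. Such a subject is a case under 7.1.1, yet 5.4 as written removes that subject.

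Two things are at stake. First, CRC cases are few, so each one removed is about 2.3% of the CRC sensitivity denominator (1/43). Second, the loss may not be neutral. If a lesion itself stops the endoscope or spoils the preparation, removal depends on the disease being studied, and the remaining cases are no longer the full disease spectrum. Sensitivity for CRC and AN and the detection rate in section 7.3 would then rest on a selected set of cases.

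**Working it through.** **Inputs from section 5.5.** Sensitivity is 0.90 for CRC and 0.80 for AA, specificity 0.90, prevalence 0.3% for CRC and 3% for AA, W = 0.09, z = 1.96.

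**Reproducing the plan's figure.** CRC cases needed: 1.96² × 0.9 × 0.1 / 0.09² = 42.7. Divided by 0.003 this gives 14,228, as stated. The design therefore implies about 43 CRCs.

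**Assumption, not in the documents.** Between 5% and 20% of CRCs have an incomplete or inadequate examination. That is 2 to 9 of 43.

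**CRC sensitivity** (section 7.1.3: "xx test sensitivity for subjects with CRC = a/(a + d")). Expected test-positives are 0.9 × 43 = 38.7. If r cases are removed and all are test-positive, sensitivity is (38.7 − r)/(43 − r). The half-width is 1.96 × √[s(1 − s)/n], with n = 43 − r. If removed cases instead test positive at the same 90%, s stays at 0.90 and only n changes.

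| r | CRCs left | Sensitivity, all removed positive | Half-width | Sensitivity, removed cases like the rest | Half-width |
|---|---|---|---|---|---|
| 0 | 43 | 90.0% | 0.090 | 90.0% | 0.090 |
| 2 | 41 | 89.5% | 0.094 | 90.0% | 0.092 |
| 4 | 39 | 89.0% | 0.098 | 90.0% | 0.094 |
| 9 | 34 | 87.4% | 0.112 | 90.0% | 0.101 |

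**AN sensitivity.** I use the 7.1.1 definition, TP/(TP + FN). At N = 14,228:
- CRC 42.7 + AA 426.8 = 469.5 AN cases.
- Test-positive: 0.9 × 42.7 + 0.8 × 426.8 = 379.9, so sensitivity is 80.9%.
- Remove 2 positive CRCs: 377.9/467.5 = 80.8%.
- Remove 9 positive CRCs: 370.9/460.5 = 80.5%.

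**AN detection rate.** The protocol gives no formula. If the denominator is unaffected by the removals, losing 2 to 9 of 379.9 detected cases lowers the rate by a relative 0.5% to 2.4%.

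**PPV for AN if confirmed cases are kept.** False positives are 0.1 × (14,228 − 469.5) = 1,375.8. Assume 5% of all examinations are incomplete, unrelated to disease (again not in the documents).
- Complete examinations only: both numerator and false positives shrink by 5%, so PPV stays at 379.9/(379.9 + 1,375.8) = 21.6%.
- Confirmed cases kept, other incomplete examinations removed: 379.9/(379.9 + 0.95 × 1,375.8) = 22.5%.

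Keeping incomplete examinations only when a lesion was found therefore raises PPV by about 0.9 points by construction.

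**Partial verification.** The figures above assume that every subject is colonoscoped. Sections 2.3 and 6.6.2 verify test-positives and only a random sample of negatives. If the number of negatives drawn equals the miR-92a positives (1,755.7 of 12,472.3, or 14.1%), crude CRC sensitivity starts near 98.5%. It moves to 98.0% with 9 positive CRCs removed. This ignores miR-92a-negative subjects verified because FIT was positive. The fall from removing 9 positive CRCs is then about 0.5 points, against 2.6 under full verification.

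**The case against.** The strongest case against the point has five parts.

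- **The text is silent, not explicit.** A reader might infer that the protocol deletes obstructing cancers as a rule, and mainly bulky or advanced ones. No section mentions obstruction, and 5.4 does not say that confirmed cases go. What the text supports is narrower: the criterion is unqualified, so literal application removes them.
- **The size rests on assumptions.** Neither the 5% to 20% range nor the premise that all removed cases test positive is in the documents. Without the second premise sensitivity is not biased. This stands.
- **AN is the main target (section 7.1.1), and there the effect is very small.** This stands, at about 0.4 points in the worst case shown. No mechanism in the documents ties AA to an incomplete examination.
- **The plan has slack.** Section 6.6 follows subjects until colonoscopy is completed, and 5.5 raises enrolment to 15,586 (16,505 in sections 1.4 and 2.3). After 5% dropout and at 0.3% prevalence, that is 44.4 to 47.0 CRCs. This offsets some or all of a loss of 2 to 4 in number. It does not put the removed cases back, and the follow-up wording does not say what happens to a case already confirmed at an incomplete examination.
- **One quality standard for everyone is defensible, and selective retention distorts PPV.** This stands for PPV. A reader might also infer that the present rule lowers PPV. It does so only if incomplete examinations are more frequent among true than false positives, which the documents do not show.

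**Conclusion.** The point holds as a gap between 5.4 and 7.1.1: an unqualified removal criterion can discard subjects whose disease is histologically known and who are cases by the protocol's own definition. Sensitivity and detection rate are affected.

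Under the assumptions stated (2 to 9 of about 43 CRCs removed, all test-positive, full verification), CRC sensitivity falls by 0.5 to 2.6 points and AN sensitivity by 0.1 to 0.4 points. If removed cases test like the rest, the cost is precision only, with the CRC half-width rising from 0.090 to between 0.092 and 0.101.

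The documents do not support reading this as a large bias, or as one that flatters miR-92a: removing test-positive cases lowers its sensitivity. They do not support keeping incomplete examinations in the main PPV either. Removal of subjects with no confirmed lesion is right, since their status is unknown and 7.1.1 would otherwise count a positive test without a confirmed lesion as a false positive. Severity is moderate.

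**What to change.** Reword the 5.4 entry along these lines: subjects with inadequate bowel preparation or an incomplete colonoscopy are removed only if neither CRC nor AA was confirmed. Then state how the retained subjects are used.

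- Confirmed CRC: keep as a CRC case and an AN case for sensitivity and detection rate.
- Confirmed AA: keep as an AN case for sensitivity and detection rate. Leave the subject out of the CRC-only analysis, because the bowel not adequately seen leaves CRC status unknown.
- Specificity and the main PPV and NPV: restrict to complete, adequate examinations. Show PPV with the retained cases as a sensitivity analysis, since selective retention raises it.
- Report the number removed under this criterion by miR-92a and FIT result, so that a reader can judge whether removal was neutral.

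The cost is one reworded criterion, a short statement of analysis sets and one extra table. No new data are needed, because section 6.7 already collects the colonoscopy, pathology and discharge information. The price is that sensitivity and PPV rest on slightly different sets of subjects, which the report should say.

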5.1 Enrolment of subjects

The target population for this study was the average risk group for CRC aged 30 – 75 years. Subjects will be recruited based on the inclusion and exclusion criteria. Subjects will be excluded if they are recruited but meet the exclusion criteria. The target population is divided into age groups of 5 years. Laboratory testing will be initiated as soon as the subject has been successfully recruited and has provided a satisfactory stool sample. The researchers will monitor the progress of the subjects and the results of the laboratory tests in real time and will count the number of enrolments and fecal-based miR-92a positivity in time to determine whether to terminate the enrolment early.

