5.3 Exclusion criteria

- History of colorectal cancer or treatment with colorectal cancer drugs or surgery;
- History of advanced adenomas or colorectal polyps;
- Patients with severe mental retardation or speech communication disorder, severe heart, brain, lung disease or liver or kidney dysfunction;
- Patients with severe ulcerative colitis;
- Patients with hereditary CRC syndromes (e.g., Lynch syndrome, FAP);
- Subjects who request to withdraw from this study;
- Subjects who are deemed unsuitable for this study by the investigator after thorough discussion.

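### Sections 5.3 and 5.4 let subjects be dropped as unsuitable at any time, unmasked, while the team sees stool and colonoscopy results, so removals could depend on the outcome

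*Protocol*

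**What the plan says.** Two clauses give the investigator discretion over who stays in the study.

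- Section 5.3 (exclusion): "Subjects who are deemed unsuitable for this study by the investigator after thorough discussion".
- Section 5.4 (removal): "Subjects who are considered unsuitable for the study after full discussion with the investigator".

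Neither names an objective ground, a latest time for the decision, masking, or an independent decision-maker. Section 5.1 says that a person already recruited is taken out if found to meet an exclusion criterion, so the Section 5.3 clause is not confined to entry.

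Other items in Section 5.4 can be judged only at or after colonoscopy: "Subjects with inadequate bowel preparation or where the colonoscope does not reach the blind part of the model" and "Subjects with an unclear diagnosis or incomplete case history".

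On access to results, Section 7.1.3 says that "the researchers will monitor the progress of enrolment, results of miR-92a and FIT, and colonoscopy and pathology results in real time". Section 5.1 says the same of laboratory results only: "The researchers will monitor the progress of the subjects and the results of the laboratory tests in real time". Section 6.7 has the investigator assemble stool, colonoscopy and pathology results in one database, and adds: "Subject enrolment, sample testing and compilation of information will be conducted simultaneously".

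**The concern.** In an accuracy study, a subject whose stool test disagrees with the colonoscopy finding counts directly against sensitivity or specificity. If the person who may declare a subject unsuitable can already see both results, a removal can, knowingly or not, follow from that disagreement. Dropping a missed case raises sensitivity; dropping a false positive raises specificity. The loss would not be visible in the final two-by-two table.

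An open-ended discretionary clause is common and mostly harmless at entry, before any result exists. Here it also operates after recruitment, in a list that extends past colonoscopy, in a study whose team follows both results as they arrive.

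**Working it through.** **Does the text permit a removal after both results are known?**

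1. Timing: Section 5.4 contains items that can be decided only at or after colonoscopy, so the list is not limited to the period before results. Section 5.1 extends the Section 5.3 criteria past recruitment.
2. Knowledge: Sections 6.7 and 7.1.3 put stool, colonoscopy and pathology results before the researchers during enrolment. The protocol does not separate researchers from investigator, and masks neither.
3. Safeguard: Section 8.3 gives a general assurance about standard procedures and database entry. It contains no rule on removals.

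Nothing in the protocol prevents such a removal.

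**Inputs (Section 5.5):** CRC prevalence 0.3%, advanced adenoma (AA) prevalence 3%, miR-92a sensitivity 90% for CRC and 80% for AA, specificity 90%, allowable error 0.09, z = 1.96.

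**The plan's own figure.** CRC cases needed = 1.96² × 0.9 × 0.1 / 0.09² = 42.68. N = 42.68 / 0.003 = 14,228, as stated.

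**Main objective, AN (Sections 7.1.1 and 7.1.3), at N = 14,228**

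- CRC: 14,228 × 0.003 = 42.7 cases, of which 0.9 × 42.7 = 38.4 detected.
- AA: 14,228 × 0.03 = 426.8 cases, of which 0.8 × 426.8 = 341.5 detected.
- AN: about 470 cases, about 380 detected; 379.9 / 469.5 = 80.9%.
- Three missed cases removed: 379.9 / 466.5 = 81.4%, a shift of 0.5 points.

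**CRC sensitivity, which sets the sample size** (illustration: 43 cases, 39 detected, every missed cancer had colonoscopy)

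| Missed cancers removed | Sensitivity |
|---|---|
| 0 | 39/43 = 90.7% |
| 1 | 39/42 = 92.9% |
| 2 | 39/41 = 95.1% |
| 3 | 39/40 = 97.5% |

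Three removals shift the figure by 6.8 points, against an allowable error of 9 points.

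**Partial verification.** Only test-positives and a random sample of negatives are sent for colonoscopy (Sections 2.3 and 6.6). Expected miR-92a positives are 38.4 + 341.5 + 0.1 × (14,228 − 469.5) = 1,756, leaving 12,472 negatives. An equal-sized draw from the miR-92a negatives, with full attendance, reaches 1,756 / 12,472 = 14% of them.

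- CRC: of four missed cancers, about 0.14 × 4 = 0.6 would be observed through that draw alone if FIT found none of them, and all four if FIT found all. The protocol gives no FIT sensitivity, so the range stays open.
- Weight per case: with one missed cancer observed, removing it moves the figure from 39/40 = 97.5% to 39/39 = 100%, or 2.5 points. The first removal in the table moves it 2.2 points.
- AN, same draw alone: about 0.14 × 90 = 13 missed cases observed. 380/393 = 96.7% becomes 380/390 = 97.4% after three removals, a shift of about 0.7 points, still small.

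**The case against.** The strongest case against has four parts.

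- **Purpose of the monitoring.** Sections 5.1 and 7.1.3 give the reason for real-time monitoring as deciding whether to stop enrolment early. No passage links it to removals, and Section 5.1 mentions laboratory results only. This is correct, and the link is one of opportunity. It stands because the protocol puts no barrier between the two.
- **The clause may be benign.** The required discussion could be an ordinary conversation with a subject who should not continue. No wording limits it to that.
- **Size.** A reader might infer that a handful of removals decides the study's main result. The protocol does not support this: the main objective is AN, where three removals shift sensitivity by about half a point. Nor is 39/43 the expected analysed table, since it takes every missed cancer as having had colonoscopy. Both limits stand, but neither removes the weight of a single case in the CRC estimate.
- **Matters for the SAP.** Tabulating removals and re-analysing with subjects restored are often left to a SAP, which is not at hand. Their absence is not the point raised here. The point is the open-ended rule that the protocol itself fixes.

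Two further inferences should be resisted. The first is that removals of this kind took place. The protocol gives 16,505 enrolled (Sections 1.4 and 2.3) and 15,586 included (Section 5.5), a difference of 919, but attributes exclusion to unqualified samples and calls none of it discretionary. The second is that the Section 5.4 clause could simply be deleted because Section 5.3 covers entry. Under Section 5.1 the Section 5.3 clause also acts after recruitment, so deletion alone would leave the permission in place.

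**Conclusion.** The point holds as a weakness in design. Sections 5.3 and 5.4, read with 5.1, 6.7 and 7.1.3, permit a discretionary removal after a subject's stool and colonoscopy results are both known. That is a statement about what the text allows, not about what was done.

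The possible effect on AN sensitivity is small: about 0.5 points for three missed cases, on the Section 5.5 assumptions with all cases verified. For CRC sensitivity it is about 2 points per missed case, and 6.8 points for three, in an illustration that assumes every missed cancer had colonoscopy. Under the partial verification actually planned, fewer missed cancers would be seen and could be removed, but each would weigh at least as much.

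**What to change.** In both Section 5.3 and Section 5.4, allow removal for unsuitability only on a written, dated decision with its reason, made either before the subject's stool results are known or by someone masked to both the stool and the colonoscopy results.

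Repeat the accuracy analysis with every discretionarily removed subject who has both a stool result and a colonoscopy result put back. Tabulate these removals by reason and by miR-92a, FIT and colonoscopy result. If there were none, the table says so.

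The cost is wording in two sections and one sensitivity analysis with its table. Section 1.5 reports the analysis as complete by the end of December 2023, so new wording cannot alter conduct already finished; the table and the repeated analysis can still be produced where the records of removed subjects were kept.
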